## **2.10. Imputation Rules for Missing Date**

In general, imputation of missing dates will be made for AE onset date, AE resolution date, start and end dates of prior and concomitant and subsequent therapies and date of initial diagnosis according to the following rules.

- If the date is completely missing, no imputation will be made.
- If the year is missing, then no imputation will be made.
- If only the year is presented but the month and day are missing, then June 30th will be used.
- If only the day is missing but the year and month are available, then the 15th of the month will be used.

In addition, for date of initial diagnosis, the imputed date will be adjusted sequentially using the following steps:

- If only the day is missing:
  - if month and year of start of 1st line of prior therapy are the same year and month of diagnosis, and day of start date of 1st line of prior therapy is available, then the day of start date of 1st line of prior therapy will be used.
  - otherwise, the 15th of the month will be used.
- If both month and day are missing:
  - if year of diagnosis is the same as year of start of 1st line of prior therapy, and month information is available for start date of the 1st line of prior therapy, the month of start date of 1st line of prior therapy will be used.
    - if day of start date of 1st line of prior therapy is available, then the day of start date of 1st line of prior therapy will be used.
    - otherwise, the 15th of the month will be used.
  - otherwise, June 30th will be used.
- If the imputed date for initial diagnosis is on or after the first dose date, then first dose date - 1 day will be used.

In addition, for date of prior and subsequent therapies, the imputed date will be adjusted sequentially using the following steps:

- If such imputed date for prior therapies is on or after the first dose date, then first dose date - 1 day will be used.
- If such imputed date for subsequent therapies is before date of last dose, then date of last dose +1 day will be used.
- If prior or subsequent therapy start date is not missing and is after the imputed end date, then the start date will be used as the end date.
- If prior or subsequent therapy end date is not missing and is before the imputed start date, then the end date will be used as the start date.

In addition, for AE date, the above imputations will be modified by the following rules:

- The imputed start date of adverse event will be adjusted sequentially using the following steps:
  - If the imputed date is in the same year and month but before the first dose date, then the first dose date will be used, or if it is in the same year and month but after the last dose date + 30 days, then the last dose date + 30 days will be used.

- If end date of adverse event is not missing and the imputed start date of adverse event is after the end date of adverse event, then the end date of adverse event will be used.
- If the imputed start date of adverse event is after date of death, then the date of death will be used.
- If the imputed start date of adverse event is in the same month and year but after the start date of 1st subsequent therapy, then the start date of 1st subsequent therapy will be used.
- The imputed end date of adverse event will be adjusted sequentially using the following steps:
  - If the imputed end date of adverse event is after the death date, then the death date will be used.
  - If the imputed end date of adverse event is before the start date of adverse event, then the start date of adverse event will be used.

In addition, for start and end dates of concomitant therapy, the adverse event imputation rule will be used for concomitant therapy.

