### 6.1. Adverse Events

The verbatim terms used in the CRF by investigators to identify adverse events will be coded using the Medical Dictionary for Regulatory Activities (MedDRA). Treatment-emergent adverse events (TEAEs) are those adverse events occurring after the first dose of study drugs and within 30 days following the last dose of study drug or initiation of subsequent antineoplastic treatment, whichever occurs earlier; any adverse event that is considered study drug-related regardless of the start date of the event; or any adverse event that is present at baseline but worsens after the first administration of study drug in severity or is subsequently considered drug-related by the investigator. If the event occurs on the day of the initial administration of study agent, and either event time or time of administration are missing, then the event will be assumed to be treatment emergent. If the event date is recorded as partial or completely missing, then the event will be considered to be treatment emergent unless it is known to be prior to the first administration of study agent based on partial onset date or resolution date. All reported treatment-emergent adverse events will be included in the analysis. For each adverse event, the number and percentage of subjects who experience at least 1 occurrence of the given event will be summarized.

Summary tables will be provided for treatment-emergent adverse events:

- Overall summary of all TEAEs
- TEAEs by System Organ Class (SOC), preferred term (PT) and toxicity grade 3 or higher
- TEAE with frequency of at least 10% by SOC, PT and toxicity grade 3 or higher
- Drug-related TEAEs by SOC, PT and toxicity grade 3 or higher
- Serious TEAEs by SOC, PT and toxicity grade 3 or higher
- TEAEs leading to dose modification (including dose interruption and dose reduction) by SOC, PT and toxicity grade 3 or higher
- TEAEs leading to discontinuation of study drug by SOC, PT and toxicity grade 3 or higher
- TEAEs leading to death by SOC and PT
- TEAEs by SOC, PT and toxicity by period
- TEAE of interest for COVID-19 infection by PT and toxicity grade
- Serious TEAE of interest for COVID-19 infection by PT and toxicity grade

- TEAE of interest for COVID-19 infection leading to death by PT

In addition to the summary tables, listings will be provided as appropriate.

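### The SAP 2.10 step that moves an imputed AE onset to first dose can never act on a year-only onset, so an event that SAP 6.1 treats as treatment-emergent can carry a pre-treatment date

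*SAP*

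**What the plan says.** SAP section 2.10 gives two general rules for partial dates. For a date known only by year: "If only the year is presented but the month and day are missing, then June 30th will be used". For a date missing only its day: "If only the day is missing but the year and month are available, then the 15th of the month will be used".

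For adverse event start dates it then lists adjustments, applied in sequence. The one that concerns first dose sets the onset to the first-dose date on this condition: "If the imputed date is in the same year and month but before the first dose date". The same bullet caps the onset at last dose plus 30 days. Later steps compare the imputed start with the event's end date ("If end date of adverse event is not missing and the imputed start date of adverse event is after the end date"), with death ("If the imputed start date of adverse event is after date of death, then the date of death will be used") and with the start of the first subsequent therapy.

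The section closes by extending these steps to concomitant drugs: "the adverse event imputation rule will be used for concomitant therapy".

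SAP section 6.1 decides treatment emergence from the partial date itself. When the onset is partly or wholly missing, "then the event will be considered to be treatment emergent unless it is known to be prior to the first administration of study agent", as judged from the partial onset date or the resolution date. Section 6.1 also plans a TEAE table by period, without defining the periods. SAP section 4.5 counts a drug as prior if it was used before first dose. It counts a drug as concomitant if it was used on or after that day, and this includes drugs begun earlier and continued.

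**The concern.** The first-dose adjustment exists so that the middle-of-interval convention does not push an onset back before treatment merely because part of the date is missing. Its same-month condition suits a missing day. A missing month is different: the imputed date is always 30 June, and the condition cannot then be met. An event with a year-only onset in the first-dose year can therefore be treatment-emergent under section 6.1 and dated before treatment under section 2.10.

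At stake are the outputs that use the imputed date: the study day in listings, any event duration computed from it, and the row's place in the by-period TEAE table. For concomitant therapy the imputed start also feeds the prior/concomitant split, and section 6.1's rule on emergence does not apply there.

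**Working it through.** The plan states no figure on this point, so the check is to run the date rules over every possible first-dose date.

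**Inputs**
- Year-only onset: 30 June of that year (SAP 2.10).
- First-dose correction: acts only if the imputed onset and first dose share both year and month, and the onset is earlier (SAP 2.10).
- Treatment emergence of a partial onset: yes, unless known to precede first dose (SAP 6.1).
- Assumption: the onset year equals the first-dose year. With an earlier onset year the event is known to be pre-treatment. With a later one, 30 June falls after first dose.

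**Step 1. Can the correction act?** It needs a first dose in June that is later than 30 June. No such date exists. Run over all first-dose dates, it acts on 0 of 365 (2019 and 2021) and 0 of 366 (2020).

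**Step 2. How many first-dose dates leave the onset before treatment?** July to December: 31 + 31 + 30 + 31 + 30 + 31 = 184 dates. That is 184/365 = 50.4%, or 184/366 = 50.3% in a leap year. For first doses from 1 January to 30 June there is no conflict.

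**Step 3. How far before treatment?** Gap = first dose minus 30 June. It is 1 day for 1 July and 184 days for 31 December. For 15 September it is 31 + 31 + 15 = 77 days, which is study day −77 by the formula in SAP 2.4.

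**Step 4. Does a later step repair it?** No. The end-date, death, subsequent-therapy and last-dose-plus-30-days adjustments all act on a start that is too late, so they can only move it earlier.

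**Step 5. Comparison with a missing day.** For an onset in the first-dose month, imputed to the 15th, the correction acts on 185 first-dose dates (186 in a leap year) and leaves none with a pre-dose onset. The rule works for the case it fits.

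**Step 6. Concomitant therapy.** Take a drug with a year-only start in the first-dose year and a first dose after 30 June. Its start becomes 30 June and stays there.
- If it is ongoing, or ends on or after first dose, SAP 4.5 keeps it concomitant and also counts it as prior.
- If its end date also resolves to before first dose (for example, also year-only in that year, hence also 30 June), it is counted only as prior and drops out of the concomitant summaries.

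**Step 7. Effect of the change.** If a year-only onset needs only the same year, the correction acts on all 184 dates from July to December, and 0 first-dose dates are left with a pre-dose onset.

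**The case against.** The strongest reply is that this hardly matters. Section 6.1 classifies on the partial date, so the overall, SOC/PT, serious, drug-related and discontinuation TEAE tables are the same either way. That stands. A reader might infer that each affected event shifts a TEAE row by 1/17, or 5.9%; the documents do not support this, because those rows do not move.

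A reader might also infer that a treatment-emergent event with a negative study day breaks the SAP's own definition. It does not. Section 6.1 already admits such events: drug-related ones whatever their start date, and baseline events that worsen. The fault is narrower. Here the early date is produced by the imputation and not by anything recorded.

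Two further inferences go too far. One is that the event fits no interval of the by-period table: the periods are undefined, so its placement is uncertain and cannot be shown to be impossible. The other is that a drug started on treatment is turned into a prior medication. Under section 4.5 it is lost from the concomitant summaries only when its end date also resolves to before first dose.

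Finally, the 50% is a share of possible first-dose dates, not of events, and the 1 to 184 days is the distance to first dose, not the error against an unknown true onset. AEs are collected prospectively from consent, with visits every 4 weeks at first, so year-only onsets may not occur at all. All of this limits the point's importance. It does not change the date logic.

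**Conclusion.** The point holds as a small error in a stated rule. The first-dose correction never acts on a year-only AE onset. With first dose from 1 July to 31 December of the onset year, an event classed as treatment-emergent keeps an imputed onset 1 to 184 days before treatment. The imputed study day, any duration derived from it and the by-period placement are affected. TEAE counts, the primary endpoint and the other efficacy results are not. For concomitant therapy the usual consequence is that a drug is counted as prior as well as concomitant; loss from the concomitant summaries is the exception.

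This rests on the onset year being the first-dose year and on the resolution date not showing that the event was over before treatment. The number of such records is not given; with about 17 subjects, few or none should be expected. The change is worth making but not essential.

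**What to change.** In SAP 2.10, for the first-dose adjustment of AE start dates, replace the same-year-and-month condition with: *in the same year (and the same month, when the month is known)*.

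A year-only onset in the first-dose year then becomes the first-dose date when 30 June precedes first dose, unless the resolution date shows that the event ended before first dose. When first dose is on or before 30 June, the onset stays at 30 June.

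The cost is one phrase and a small loss of accuracy in one direction: an event that truly began earlier in that year would be dated to first dose. That matches the default section 6.1 already applies.

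Because section 2.10 carries the AE rule to concomitant therapy, the SAP should say whether the new wording applies there. If it does, state that a drug truly started earlier in that year would no longer be counted as prior. Check the last-dose-plus-30-days and subsequent-therapy adjustments separately before changing them; the result in step 7 covers only the first-dose adjustment.

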### 3. INTERIM ANALYSIS AND DATA MONITORING COMMITTEE REVIEW

No interim analysis will be conducted in this study.

### 4. SUBJECT INFORMATION

The number of subjects in each analysis set will be summarized.

#### 4.1. Demographics and Baseline Characteristics

List of the demographic and baseline characteristics, presented in [Table 1](#), will be summarized for the all treated analysis set.

**Table 1: Demographic and Baseline Characteristic Variables**

Continuous Variables:	Summary Type
Age (years)	Descriptive statistics (N, mean, standard deviation [SD], median and range [minimum and maximum].)
Weight (kg)	
Height (cm)	
Baseline hemoglobin (g/L)	
Baseline platelets ( $10^9/L$ )	
Baseline absolute neutrophil count ( $10^9/L$ )	
Aspartate Aminotransferase (AST) (U/L)	
Alanine Aminotransferase (ALT) (U/L)	
Total bilirubin (umol/L)	
Baseline creatinine (umol/L)	
Baseline creatinine clearance rate (mL/min)	
Categorical Variables	
Age (<=65, and >65 years)	Frequency distribution with the number and percentage of subjects in each category.
Sex (male, female, undifferentiated)	
Baseline creatinine clearance rate (<30mL/min, 30-<60mL/min, >=60mL/min)	
Baseline liver function based on NCI criteria a (Normal, Mild, Moderate and Severe)	

**Table 1: Demographic and Baseline Characteristic Variables**

Continuous Variables:	Summary Type
a: Mild (total bilirubin $\leq$ ULN and AST $>$ ULN) or (ULN $<$ total bilirubin $\leq$ 1.5 $\times$ ULN); moderate (1.5 $\times$ ULN $<$ total bilirubin $\leq$ 3 $\times$ ULN); and severe (total bilirubin $>$ 3 $\times$ ULN).	

Following baseline disease characteristics information will be summarized for all treated subjects:

- Month from initial diagnosis, which is defined as the time period between date of initial WM diagnosis and date of first dose of study drug.
- ECOG performance grade (0-1, 2)
- Number of prior systemic treatment regimens (1-2, >-3)
- Serum IgM
- Monoclonal protein spike
- Beta-2 microglobulin
- Extramedullary disease (adenopathy, splenomegaly)
- Longest diameter of spleen
- Sum of products of diameters - target nodal lesions
- Tumor involvement of the bone marrow by: Cellularity
- Intertrabecular space (percentage of total bone marrow cells within intertrabecular space)
- Cytopenia (hemoglobin  $\leq$ 110 g/L, platelets  $\leq$ 100 $\times$ 10 $^9$ /L, absolute neutrophil count  $\leq$ 1.5 $\times$ 10 $^9$ /L)

#### 4.2. Disposition Information

The number of subjects in the following disposition categories will be summarized throughout the study:

- Subjects screened
- Subjects received study agent
- Subjects who is still on treatment at CCO
- Subjects who discontinued study agent
- Reasons for discontinuation of study agent, including COVID-19 related reasons
- Subjects who terminated study prematurely
- Reasons for termination of study

Listings of subjects will be provided for the following categories:

- Subjects who discontinued study agent
- Subjects who terminated study prematurely

Subjects who discontinue from treatment or study due to COVID-19 related reasons will be listed.

#### **4.3. Extent of Exposure**

Extent of exposure to study treatment will be summarized and presented based on the safety analysis set. Descriptive statistics (N, mean, SD, median, and range [minimum, maximum]) will be presented for the following parameters:

- Treatment duration (month)
- Cumulative total dose (g)
- Dose intensity (mg/day)
- Relative dose intensity
- Time on study (month)

The number (%) of subjects with a study drug modification (dose skip and/or dose reduction) will be summarized. Reasons for study drug modifications will also be summarized.

#### **4.4. Protocol Deviations**

In general, the following list of major protocol deviations may have the potential to impact subjects' rights, safety or well-being, or the integrity and/or result of the clinical study. Subjects with major protocol deviations (including COVID-19 related deviations) will be identified prior to database lock and the subjects with major protocol deviations will be summarized by category for all treated analysis set.

- Entered but did not satisfy inclusion/exclusion criteria
- Received a disallowed concomitant treatment
- Received incorrect dose
- Developed withdrawal criteria but not withdrawn
- Efficacy assessment deviation
- Safety assessment deviation

#### **4.5. Prior and Concomitant Medications**

Concomitant medications will be coded using the World Health Organization Drug Dictionary (WHO-DD). Prior medications are defined as any therapy used before the first dose of the study drug. Concomitant medications are defined as any therapy used on or after the same day as the first dose of study drug, including those that started before and continue on after the first dose of study drug.

Summaries of prior and concomitant medications will be presented by therapeutic class and preferred term for all treated analysis set. In addition, the following concomitant medications will be summarized separately: growth factors, blood supportive products and immunoglobulin,

CYP3A inhibitors (strong, moderate and weak), CYP3A inducers, anticoagulants and/or antiplatelets and subsequent antineoplastic therapy.

In addition, concomitant medication for COVID-19 infection will be listed.

#### **4.6. Medical history**

Medical history collected at baseline or screening visit will be summarized by system-organ class and preferred term for all treated population.

### **5. EFFICACY**

#### **5.1. Analysis Specifications**

##### **5.1.1. Level of Significance**

All tests will be 1-sided. The primary efficacy endpoint will be tested at the overall significance level of 0.05. For result presentation purpose, a 2-sided 90% confidence interval will be used.

##### **5.1.2. Data Handling Rules**

Unless specified otherwise, missing values will not be imputed, and partial dates are described in Section 2.10.

#### **5.2. Primary Efficacy Endpoint(s)**

The primary efficacy endpoint is ORR by investigator assessment.

##### **5.2.1. Definition**

ORR is defined as the proportion of subjects who achieve PR or better per the modified Consensus Response Criteria from the VIth IWWM (NCCN 2019).

##### **5.2.2. Analysis Methods**

The all treated analysis set will be used for primary endpoint.

The primary analysis for primary endpoint will be conducted at the time of approximately 12 months after the last subject receives first dose. Final analysis will be conducted at the study end, which is estimated to occur 3 years after last subject receives first dose.

The overall response rate (PR or better) and its 90% confidence interval will be calculated with the exact test for binomial distribution in the all treated population. The study is considered to be positive if the lower limit of the exact 2-sided 90% confidence interval based on binomial distribution exceeds the threshold value (0.32).

##### **5.2.3. Primary Estimand**

**Primary Trial Objective:** To evaluate the efficacy of ibrutinib in Chinese patients with relapsed or refractory WM.

**Primary Estimand Scientific Question of Interest:** What is the effect on overall response rate of assigning ibrutinib to Chinese relapsed or refractory WM subjects?

The primary estimand, the main clinical quantity of interest to be estimated in the study, is defined by the following 5 components:

- **Population:** Chinese subjects with relapsed or refractory Waldenstrom's Macroglobulinemia who have received at least one prior therapy for Waldenstrom's Macroglobulinemia and have had either documented disease progression or had no response (stable disease) to the most recent treatment regimen.
- **Variable:** Overall response
- **Treatment:** Ibrutinib 420 mg orally, once daily
- **Summary measure:** Overall response rate
- **Intercurrent Events (IEs) and Corresponding Strategies:**

Intercurrent Events	Name of Strategy for Addressing Intercurrent Events and Its Description
Subsequent anti-cancer therapy	While on Treatment Strategy , targeting a treatment effect prior to the initiation of subsequent anti-cancer therapy.
Treatment discontinuation	Treatment Policy Strategy , targeting a treatment effect regardless of this IE.

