Quantitative serum immunoglobulins (IgA, IgG and IgM)	X	X	X	X	X	X	X	X	X	
Serum free light chain assay	X					Weeks 49 and 97	X			
Bone marrow aspirate and biopsy l	X					Weeks 49 and 97 (± 2 weeks)	X	X		

	Screening Phase	Treatment Phase							Post-Treatment/ Follow-Up Phase	
		1	5-16 q4 weeks	17	21	25+ q8 weeks	Suspected PD Visit	End-of-Treatment Visit a	Post-treatment Pre-disease Progression Phase q12 weeks	Post-disease Progression Phase q12 weeks
Study Weeks		1	5-16 q4 weeks	17	21	25+ q8 weeks	Suspected PD Visit	End-of-Treatment Visit a	Post-treatment Pre-disease Progression Phase q12 weeks	Post-disease Progression Phase q12 weeks
Study Day of the Study Week		1	1	1	1	1				
Study Windows	-30 days		± 3 days		± 3 days	± 3 days	Anytime	± 7 days	± 7 days	± 7 days
CT Scans	X i			X j		X i	X k		X j	
Overall disease assessment			X	X	X	X	X	X	X	
Survival status, new anticancer therapy and occurrence of other malignancy m									X	X
PK sampling										
PK h		X	Weeks 5 and 9							
Ongoing Subject Assessments										
Concomitant medications	X	Continuous from Informed Consent to 30 days after last dose of study drug								
Adverse events	X	Continuous from Informed Consent to 30 days after last dose of study drug								

Abbreviations: aPTT=activated partial thromboplastin time; CR= complete response; CT=computed tomography; DNA=deoxyribonucleic acid; ECG=electrocardiogram; ECOG=Eastern Cooperative Oncology Group; eCRF=electronic case report form; EOT=end-of-treatment; ICF=informed consent form; IEC=Independent Ethics Committee; INR=international normalized ration; IRB=Institutional Review Board; PCR=polymerase chain reaction; PD=progressive disease; PK=pharmacokinetic(s); PO=orally; PT=prothrombin time; q4 weeks=every 4 weeks; q8 weeks=every 8 weeks; q12 weeks=every 12 weeks; REB=research ethics board.

- a. Thirty (30) days from last dose of study drug or prior to the start of a new anticancer treatment.
- b. All subjects must first read, understand, sign and date the IRB/REB/IEC-approved ICF before any study-specific screening procedures are performed.
- c. Physical Examination includes: general appearance of subject, height (screening only) and weight and examination of skin, eyes, ears, nose, throat, lungs, heart, abdomen, extremities, musculoskeletal system, lymphatic system, and nervous system.

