#### 5.3.1. Definition

##### Clinical response rate:

CRR is defined as the proportion of subjects who achieve MR or better according to the modified IVth IWWM (NCCN 2019) criteria as assessed by the investigator.

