##### Very good partial response (VGPR) or better rate:

VGPR or better rate is defined as the proportion of subjects who achieve VGPR or better according to the modified IVth IWWM (NCCN 2019) criteria as assessed by the investigator.

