**Duration of response (DOR):**

DOR is defined as duration from the date of initial documentation of a response (PR or better) to the date of first documented evidence of progressive disease, death or date of censoring if applicable, for responders (PR or better) as assessed by the investigator. DOR will be right censored based on [Table 2](#) for all responders:

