**Time to response:**

Time to response is defined as the time from the date of first dose to the date of initial documentation of a response (PR or better) for responders.

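### Do the ORR and secondary response definitions need their own cut-off at the start of subsequent anti-cancer therapy, beyond the one in SAP 5.2.3?

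*SAP*

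**What the plan says.** SAP 5.2.3 (Primary Estimand) names two intercurrent events for ORR. For subsequent anti-cancer therapy it uses a while-on-treatment strategy, "targeting a treatment effect prior to the initiation of subsequent anti-cancer therapy". For treatment discontinuation it uses treatment policy. A response documented after ibrutinib is stopped therefore still counts, provided no new therapy has begun.

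The other response texts in the SAP give no such limit:

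- 5.2.1: "ORR is defined as the proportion of subjects who achieve PR or better per the modified Consensus Response Criteria from the" VIth IWWM.
- 5.2.2: "The overall response rate (PR or better) and its 90% confidence interval will be calculated with the exact test for binomial distribution", in all treated subjects, with success if the lower limit exceeds 0.32.
- 5.3.1, CRR: "CRR is defined as the proportion of subjects who achieve MR or better according to the modified" IWWM criteria.
- 5.3.1, VGPR or better: "VGPR or better rate is defined as the proportion of subjects who achieve VGPR or better according to the modified" IWWM criteria.
- 5.3.1, DOR: measured "for responders (PR or better) as assessed by the investigator".
- 5.3.1, TTR: measured to "the date of initial documentation of a response (PR or better) for responders".

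SAP Table 2 is explicit on a different matter: progression or death counts as a DOR or PFS event whether or not other antineoplastic therapy came first.

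On data collection, Protocol 9.1.4.1 keeps subjects who stop for reasons other than progression on 12-weekly clinic visits until progression, even if new treatment has started. The Time and Events Schedule marks SPEP, quantitative immunoglobulins and "Overall disease assessment" in that phase. Protocol 9.2 asks that new therapy wait for confirmed progression where this can be done.

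**The concern.** The estimand restricts ORR in time, but the definition and analysis of the same endpoint do not, and neither do four further definitions that depend on response. The data that would expose the difference can exist. A subject may stop ibrutinib for toxicity, start another drug before progression, and have IgM and disease status assessed on that drug.

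A programmer working only from the definitions could credit ibrutinib with a response due to another agent. Two sequences matter:

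- **Deepening after a switch.** A subject already in PR reaches VGPR on the new drug. ORR does not move; VGPR or better rises by one.
- **First PR after a switch.** ORR, TTR and the DOR responder set would all change. If the limit were applied to ORR alone, this subject would be a non-responder for ORR yet a responder for DOR and TTR.

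In a trial of about 17 subjects meant to support full approval in China (Protocol 1.2), one subject is visible in any rate.

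**Working it through.** **Step 1. Reproduce the design figure.** Inputs from SAP 1.4, 5.1.1 and 5.2.2: N = 17, null ORR 0.32, assumed ORR 0.698, 1-sided alpha 0.05, success if the exact 90% lower limit exceeds 0.32. The Clopper-Pearson limits for x responders are: lower = the 0.05 quantile of Beta(x, 17 − x + 1); upper = the 0.95 quantile of Beta(x + 1, 17 − x).

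- 9/17 = 52.9%: lower limit 31.1%, fails; P(X ≥ 9 | 0.32) = 0.059.
- 10/17 = 58.8%: lower limit 36.4%, passes; P(X ≥ 10 | 0.32) = 0.020.
- Power: P(X ≥ 10 | 0.698) = 89.2%, which meets the stated minimum of 85%.

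None of these figures depends on the point at issue, which concerns who is a responder.

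**Step 2. Set the texts side by side.**

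| Endpoint | Limit in its own text? | Does a rule reach it? |
|---|---|---|
| ORR (SAP 5.2.1, 5.2.2) | No | Yes: 5.2.3, same section, same endpoint |
| DOR responders (5.3.1) | No | Yes, by natural reading: the PR-or-better subjects of ORR |
| TTR (5.3.1) | No | Yes, same reading |
| CRR (5.3.1) | No | Not stated |
| VGPR or better (5.3.1) | No | Not stated |
| DOR and PFS events (Table 2) | Own explicit rule | Counts events despite new therapy; does not define responders |

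For ORR, 5.2.1 and 5.2.2 are silent and 5.2.3 speaks. Silence in one subsection does not contradict a rule in the next. The open cells are CRR and VGPR or better. Protocol 11.3.2.1 and 11.3.2.2 tie them to ORR only in how the exact interval is calculated, so those sections do not settle which assessments count.

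**Step 3. Who could be affected?** The case needs, in order: a stop for a reason other than progression; new therapy before progression, despite Protocol 9.2; and then a higher response category reached for the first time before progression. After progression, Protocol 9.1.4.2 provides only for survival, new therapy and other malignancies. A subject with MR or better before the switch cannot move CRR. A subject with VGPR before the switch cannot move VGPR or better.

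**Step 4. Size per subject.** The counts below are assumed, because the documents give no number of switchers. One subject moves a rate by 1/17 = 5.9 points.

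- VGPR or better, 2/17 to 3/17: 11.8% (90% CI 2.1 to 32.6) to 17.6% (5.0 to 39.6).
- ORR, 11/17 to 12/17, only if 5.2.3 were ignored: 64.7% (42.0 to 83.4) to 70.6% (47.8 to 87.6). Both pass 32%.

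**Step 5. What ignoring 5.2.3 could do to the primary test.** Suppose a share s of subjects without a prior PR start new therapy before progression, and a share q of those then reach PR. At a true ORR of 0.32 the counted rate becomes 0.32 + 0.68 × s × q, and the chance of a positive study is P(X ≥ 10) at that rate.

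- No switchers: 0.320, chance 2.0%.
- s = 5%, q = 32%: 0.331, chance 2.6%.
- s = 10%, q = 50%: 0.354, chance 4.1%.
- s = 20%, q = 70%: 0.415, chance 11.5%.

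The values of s and q are assumptions. The inflation arises only from analysing ORR against the SAP's own estimand; following 5.2.3 removes it.

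**The case for a change.** The best case for a change is that the rule should be explicit before any affected subject is known. Section 5.2.3 is headed as the primary estimand, so it does not on its face govern CRR or VGPR or better. The cut cannot be taken from the end of treatment either, because discontinuation is under treatment policy; the date that matters is the start of new therapy. The final analysis, 3 years after the last first dose, leaves more time for switches than the primary cutoff. A sentence would cost almost nothing, since SAP 2.10 already covers incomplete subsequent-therapy dates.

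Much of this stands as description. SAP 5.3.1 does not say whether a category first reached after new therapy counts for CRR and VGPR or better, and stating it would do no harm. It does not make the plan defective. These two rates lie outside the primary estimand, so they do not conflict with it. They carry no threshold, so no conclusion turns on them. One response derivation for ORR, CRR and VGPR or better is the ordinary way to build such data, and it keeps VGPR or better a subset of ORR and ORR a subset of CRR. Table 2 does not argue against this, because it governs events and censoring, not who is a responder.

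**Conclusion.** No change is needed. The time limit for ORR is already in SAP 5.2.3, and the DOR and TTR responder sets naturally follow ORR. What remains is a missing detail for two descriptive rates, which an analyst would very likely fill by using the same assessments as for ORR.

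The size is 5.9 points per affected subject on CRR or VGPR or better. The number affected is unknown, limited by the sequence in Step 3, and may be zero. The success boundary of 10/17, the exact alpha of 0.020 and the power of 89.2% are untouched.

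This conclusion rests on two assumptions: that ORR is programmed with 5.2.3 applied, and that responders in the DOR and TTR definitions means the ORR responders. Both are the plain reading of the SAP.
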